Overall, among 420 participants, on a scale of 0-10 (zero being no pain and 10 being the most imaginable pain), 67% of participants reported feeling no pain, 26% of participants reported pain of 1, 5% reported pain of 2, and 2% of participants reported feeling pain at a 3 or higher with 5 being the highest reported pain. Ninety-five percent of all participants reported to prefer the Tasso+™ blood collection method to venipuncture and finger stick, and 95% of participants reported they would be willing to use the Tasso device at least monthly ([Tasso, Investigator Brochure, September 2023](#)).

Recently, a multi-center, unblinded, longitudinal observational study of enabling technologies for COVID-19 surveillance (including the Tasso) was conducted with the objective to provide surveillance through enabling technologies to describe physiological parameters, symptoms, respiratory fluid virus levels, and host immune and inflammatory responses in enrolled subjects ([JPEO-003, Summary of Results, 2022](#)).

Overall, 62 participants (52 with mild to moderate COVID-19 and 10 healthy controls) were enrolled at 2 clinical sites in the US beginning in July 2021 and completing follow-up in January 2022. The age of participants ranged from 18 to 90 years in the COVID-19 group (57.7% female) and from 18 to 53 years in the Control group (60% female). Median age in both groups was 30 years. In the COVID-19 group, 18 of 52 participants (34.6%) had previously received COVID-19 vaccine; 7 of 10 in the Control group (70.0%) had previously been vaccinated for the disease. The days from last vaccine dose to enrollment ranged from 21 to 319 days (median 236.5) in the COVID-19 group and from 71 to 305 days (median 193) in the Control group.

Regarding accuracy of Tasso sample against venous sample: control group participants were uniformly antibody positive at all visits in tests performed with venous whole blood or Tasso whole blood. For COVID-19 group participants, 27/48 (56.2%) were positive on Day 1, with progressive increases in positivity rate at each visit to 48/49 (98.0%) on Day 29. Similar results were obtained using Tasso whole blood, but the antibody positivity rate and median antibody cutoff values were lower with Tasso whole blood than with venous whole blood ([Table 3](#)).

Table 3 Summary of LightDeck Antibody Results (Venous Whole Blood vs Tasso Whole Blood) (JPEO-003, Summary of Results, 2022)

	COVID-19 group (n=49)			Control group (n=10)		

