Examples of Tasso device use for SARS-CoV-2 antibody testing have been published in the literature. In one study, the use of Tasso device for capillary blood self-collection was associated with a high success rate (93.4% of participants in unsupervised settings and 94.5% of participants in supervised settings) and an excellent concordance (overall accuracy of 98.9%) for anti-SARS-CoV-2 IgG results when compared to standard venous blood-derived sera ([Hendelman et al., 2021](#)). In another study, 70.0% of participants were able to collect an adequate sample for testing using the Tasso device. Among those with an adequate sample, there was a high concordance in results between the Tasso/SST and phlebotomy blood collection methods (Cohen's kappa coefficient = 0.88). Moreover, the

Tasso device receives a high-level (90.0%) of acceptance among all participants ([Wixted et al., 2022](#)). To note, the higher failure rate (30.0%) observed by [Wixted et al., \(2022\)](#) compared to the failure rate of 6.6% observed by [Hendelman et al., \(2021\)](#) could be due to an older population (median age and range of 58.0 years [45.0 to 68.0 years] vs 45 years [21 to 73 years]), in which manual dexterity or comorbidities could be more likely to affect use of the device.

The Tasso+™ lancet is an enabling technology that is an FDA 510(k)-cleared Class II medical device that aims to improve upon the traditional venipuncture blood collection experience. This study aims to evaluate the third generation Tasso+™ device with Tasso+™/SST and Tasso+™/EDTA collection kits with respect to device performance and user experience in adult participants who are healthy or in well-compensated health. The Tasso+™/SST collection kit will be used to evaluate serum while the Tasso+™/EDTA collection kit will be used to evaluate whole anticoagulated blood and plasma.

The laboratory results of Tasso+™/SST capillary collection tube will be compared on Day 1 to blood collected using the standard venipuncture by an HCP across an array of laboratory tests being tested by laboratory technicians at a single central laboratory ([Table 4](#)).

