Establishing correlation coefficients of laboratory results collected by a study participant and compared to standard venipuncture will be an important milestone to rely solely on the patient/study participant to self-collect blood using either device/kit collected and to ship the samples to a designated laboratory. Indeed, in a recent study, even though Tasso/SST serum protein measurements were highly reproducible, self-collection at home with delayed sample processing was associated with significant concentration differences for several analytes compared to supervised, in-clinic collection with rapid processing ([Brandsma et al., 2022](#)). These results are to be compared to higher concordance results obtained among other studies focusing on serology: overall accuracy of 98.9% in the study conducted by [Hendelman et al., \(2021\)](#) and Cohen's kappa coefficient of 0.88 in the study conducted by [Wixted et al., \(2022\)](#).

The sample integrity of Tasso+™/SST (ie, adequate volume and absence of moderate or gross hemolysis) and Tasso+™/EDTA (ie, adequate volume, absence of moderate or gross hemolysis, and absence of clotting) capillary collection tubes will be evaluated on Day 1 for each cohort and on each of Days 29 and 57 for Cohorts A and B combined ([Table 4](#)).

Table 4 Sample Testing Table

Method of blood collection	Laboratory Results		Sample Integrity		
	SARS-CoV-2	Chemistry*	Sample Volume	Hemolytic Index	Clotting
Tasso+™ device	EDTA	✓	✓	✓	✓
	SST	✓	✓	✓	✓
Venipuncture	EDTA	✓			
	SST	✓	✓		

EDTA=ethylenediaminetetraacetic acid; SST=serum separator tube

Footnotes: Chemistry analytes include sodium, potassium, chloride, blood urea nitrogen, creatinine, glucose, phosphate, uric acid, and C-reactive protein.

There will be no complete blood count laboratory analysis using Tasso+™/EDTA capillary collection tube due to potential for red cell lysis and clotting, and insufficient blood volume collection that may preclude accurate results.

The impact of the timing of centrifugation after blood collection with Tasso+™ on blood sample integrity and accuracy will be evaluated on Day 1, as Tasso+™ blood samples of Cohort A participants will be centrifuged after shipping to the Central Laboratory, while Tasso+™ blood samples of Cohort B participants will be centrifuged and aliquoted by the Site prior to being shipped to the Central Laboratory alongside with venipuncture blood samples that will be centrifuged prior to shipping as per standard procedures.

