6.3.2 Testing Accuracy

Testing accuracy of the Tasso+™ device, as part of device performance, will be evaluated as (i) the correlation of SARS-CoV-2 serology between venipuncture and either Tasso+™/SST or Tasso+™/EDTA samples collected on Day 1; and (ii) the correlation of each chemistry analyte between venipuncture and Tasso+™/SST samples collected on Day 1. This endpoint will only be assessed on Day 1 for each cohort separately.

Seroconversion will be evaluated using IgG Nucleocapsid assay. A total serum (SST) or plasma (EDTA) volume of 175 µL will be necessary to cover potential retesting, if needed. Any participant who is positive for IgG Nucleocapsid assay for either matrix (SST or EDTA), will be considered SARS-CoV-2 positive.

The following chemistry analytes will be assessed for correlation between the two collection approaches (venipuncture and Tasso+™/SST) on Day 1: sodium, potassium, chloride, blood urea nitrogen, creatinine, glucose, phosphate, uric acid, and C-reactive protein.

Noteworthy, in case of long duration between sample collection and testing, there may be risks associated with inaccurate sodium, potassium, and glucose values.

If a sodium, potassium, or glucose level is determined by the PI to be possibly clinically significant, a venipuncture repeat of the test should be performed at the Investigator site for safety reasons. Testing will be performed by the Investigator site and will not be sent to the Central laboratory.

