9.5.2.2 Testing Accuracy

Pearson's correlation coefficient will be computed to quantify the strength of the direction of the linear relationship between the venipuncture collection and the Tasso+™ collection at Day 1 for each cohort for SARS-CoV-2 serology and each chemistry analyte.

Any participant who is positive for IgG Nucleocapsid assay for either matrix (SST or EDTA), will be considered SARS-CoV-2 positive.

Contingency correlation coefficient will be computed to estimate the extent of the relationship between the venipuncture collection and the Tasso+™ collection at Day 1 for each cohort for SARS-CoV-2 serology.

This analysis will be presented for both the FAS and PPS.

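### Day 1 positive/negative serology is summarised by a contingency coefficient that, in its usual form, is unsigned, cannot exceed 0.707 and does not report missed positives; paired agreement rates should be added

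*SAP*

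**What the plan says.** Protocol 6.3.2 defines the endpoint: "Testing accuracy of the Tasso+™ device, as part of device performance, will be evaluated as (i) the correlation of SARS-CoV-2 serology between venipuncture" and the Tasso+/SST or Tasso+/EDTA sample, on Day 1, by cohort. Protocol 3.1 lists it among the primary endpoints. Protocol 9.4.1.2 names only Pearson's correlation as the method.

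SAP 9.5.2.2 plans two statistics for serology, in the FAS and PPS:

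- Pearson's, where the "correlation coefficient will be computed to quantify the strength of the direction of the linear relationship between the venipuncture collection and the" Tasso+ collection. It covers serology and every chemistry analyte. The SAP does not say whether the serology input is a numeric assay value or a 0/1 result.
- A second measure: "Contingency correlation coefficient will be computed to estimate the extent of the relationship between the venipuncture collection and the" Tasso+ collection, for serology. No formula, adjustment or maximum is given.

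Between the two stands the rule for the binary result: "Any participant who is positive for IgG Nucleocapsid assay for either matrix (SST or EDTA), will be considered SARS-CoV-2 positive".

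Neither document plans a paired 2x2 table, percent agreement (overall, positive or negative) or kappa. SAP 9.5.1 states that hypothesis testing does not apply, and no acceptance threshold is set.

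**The concern.** The question behind the endpoint is whether a Tasso+ tube gives the same serology answer as a venous tube and, if not, which way it errs. A contingency coefficient measures association. It responds equally to agreement and to its mirror image, its ceiling for a 2x2 table is well below 1, and it merges missed and false positives into one number.

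Two consequences follow. First, a reader who assumes a 0-to-1 scale may take near-perfect agreement for a moderate result, because the SAP gives no maximum. Second, the planned output contains no rate of missed positives. The either-matrix rule adds to this: if the SST tube misses a positive and the EDTA tube detects it, the participant still counts as positive, so a participant-level table can hide a miss in one tube type, although the endpoint names both.

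The study is descriptive, so these summaries are the whole result for this endpoint.

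**Working it through.** **Inputs.** Cohort sizes are 133 (A) and 67 (B), from SAP 6.2. The share of seropositive participants is not given; I assume 50% to 95%. All tables are illustrative. The documents state no value for the coefficient, so there is no figure to reproduce.

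**Formulae.** Let a = both positive, b = Tasso+ positive only, c = venous positive only (missed), d = both negative.

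- phi = (ad − bc) / √[(a+b)(c+d)(a+c)(b+d)], and chi² = n·phi²
- C = √[chi²/(chi² + n)] = |phi| / √(1 + phi²)
- Positive agreement = a/(a+c); negative agreement = d/(b+d); overall = (a+d)/n

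**Ceiling.** |phi| is at most 1, so C is at most 1/√2 = 0.7071.

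**Direction and type of error.**

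| a/b/c/d | n | Overall | Positive agr. | Negative agr. | phi | C |
|---|---|---|---|---|---|---|
| 67/0/0/66 | 133 | 100% | 100% | 100% | 1.00 | 0.7071 |
| 0/66/67/0 | 133 | 0% | 0% | 0% | −1.00 | 0.7071 |
| 63/4/4/62 | 133 | 94.0% | 94.0% | 93.9% | 0.880 | 0.6605 |
| 4/62/63/4 | 133 | 6.0% | 6.0% | 6.1% | −0.880 | 0.6605 |
| 59/0/8/66 | 133 | 94.0% | 88.1% | 100% | 0.886 | 0.6633 |
| 55/0/5/7 | 67 | 92.5% | 91.7% | 100% | 0.731 | 0.5903 |

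For the fifth row: phi = (59×66)/√(59×74×67×66) = 3894/4393.9 = 0.8862, and C = 0.8862/√(1 + 0.7854) = 0.6633. Rows 3 and 5 differ by 5.9 percentage points in positive agreement and by 0.003 in C.

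**Where close agreement lands.** At 98.9% overall agreement with errors split evenly, C is 0.6992, 0.6977, 0.6845 and 0.6624 at 50%, 70%, 90% and 95% positive. A kappa of 0.88 with equal margins means phi = 0.88, so C = 0.88/√(1 + 0.7744) = 0.6606.

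**Dependence on the share of positives.** Hold positive agreement at 92% and negative agreement at 98%. C is 0.670 at 50% positive and 0.584 at 90% positive. Kappa moves too, from 0.90 to 0.69.

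**One method uniform.** Take 67 venous positives with 3 missed (a = 64, c = 3). Then b + d = 0, so phi, C and Pearson's r on 0/1 data are undefined. Positive agreement is 64/67 = 95.5%. Kappa is 0.00, because expected agreement (64×67)/67² = 64/67 equals observed agreement.

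**Pearson's r.** On 0/1 results r equals phi: it is signed and reaches ±1, but it does not report the two error rates. On numeric values it does not use the cut-off, and if every Tasso+ value is 0.7 times the venous value, r = 1.00 despite a uniform 30% under-reading.

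**The case against.** The strongest reply is that the coefficient does not stand alone. On 0/1 results the planned Pearson correlation would be −1 for a full reversal and is not capped at 0.707. That stands, provided r is applied to 0/1 results, which the SAP leaves open. A reader might infer that the plan cannot tell agreement from reversal; that is true of the contingency coefficient, not of the plan as a whole. Full reversal is also implausible for paired samples tested at one central laboratory.

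Four further inferences go beyond the documents:

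- *That the trial has set itself benchmarks it cannot meet on this scale.* Protocol 1.2 cites one study with "excellent concordance (overall accuracy of 98.9%) for anti-SARS-CoV-2 IgG results when compared to standard venous blood-derived sera" and another with "kappa coefficient = 0.88". The later sentence "These results are to be compared to higher concordance results obtained among other studies focusing on serology" refers back to a published protein-measurement study and contrasts it with other publications. These are background figures, not criteria for this trial.
- *That the earlier study already shows missed positives on Day 1.* Protocol 1.1.3 does report lower positivity with Tasso whole blood, but Table 3 shows 27 of 48 positive by both methods on Day 1. The differences appear on Days 4 and 8, and this endpoint is Day 1 only.
- *That an undefined coefficient is likely.* The statement that "control group participants were uniformly antibody positive at all visits" concerns 10 controls on a different assay. The same study's COVID-19 group was 56.3% positive on Day 1 by venous blood. The case is possible, but nothing supports it for this population.
- *That the miss rate cannot be known.* It is unplanned, not unobtainable, since the paired results are collected.

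It is also fair to say that the protocol words the endpoint as a correlation, so the SAP follows it. That explains the choice but does not supply agreement rates.

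**Conclusion.** The point holds for the coefficient and for the missing output. As planned, the serology accuracy endpoint would be reported on a scale where close agreement reads about 0.66 to 0.70, where 8 misses and a 4-and-4 split of errors look alike, and with no rate of missed or false positives beside it. The Pearson correlation removes part of the difficulty (direction, if computed on 0/1 results) and leaves the rest.

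This rests on two assumptions: the unadjusted coefficient, and a strictly two-category result. A third result category would raise the ceiling to √(2/3) = 0.816. A maximum-adjusted version or Cramér's V would reach 1 but would remain unsigned as computed from chi-square. The size of the effect in this trial depends on a seropositive share that the documents do not give. The data are unaffected; only their summary is.

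**What to change.** In SAP 9.5.2.2:

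- Add, for each cohort, the paired 2x2 table against venipuncture with positive, negative and overall percent agreement and exact 95% confidence intervals. Do this separately for Tasso+/SST, for Tasso+/EDTA and for the either-matrix result. Name these as the main serology accuracy summary.
- Drop the contingency coefficient for serology, or keep it as supplementary with its formula and 0.707 maximum stated.
- Treat kappa as optional, with a note that it depends on the share of positives and can be zero at high agreement.
- State that Pearson's r for serology applies to numeric assay values, if these are reported.

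The cost is SAP wording and a few routine tables from data already collected. The one drawback is that negative agreement will be imprecise if few participants are negative. With 7 of 7 negatives agreeing, for example, the exact lower limit is 0.025^(1/7) = 0.59. The interval would show that openly.

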9.5.2.3 Reliability

For each participant, the number of failures will be calculated by summing the instances where the device or the collection process has failed as follows:

- (i) failure in activation of the lancet
- (ii) lack of any blood collection within 5 minutes
- (iii) incorrect attachment of the capillary collection tube to the device
- (iv) damage to the device or the capillary collection tube upon handling
- (v) lack of maintained seal between the device and the skin surface of the participant
- (vi) incomplete trigger of the button (not fully pressing the button once the Tasso+™ device is sealed to the skin surface)

The total number of device usage instances will also be recorded.

The percentage of failures will be calculated as:

$$\text{Percentage of failures} = \frac{\text{Number of Instances with Failures}}{\text{Total Number of Device Usage Instances}} \times 100\%$$

Counts and percentages will be presented for participants in the FAS and PPS.

9.5.3.2 Tolerability

The count and percentage of participants in the FAS who completed their Day 57 Tasso+™ administration will be summarized, where completion is defined as having completed at least one of Tasso+™/SST or Tasso+™/EDTA at the visit.

9.5.3.3 Usability

Descriptive statistics will be presented for participants in the FAS for each aspect of the usability questionnaire on Days 1, 29, 57 and 85.

9.5.3.4 SARS-CoV-2 Infection Surveillance

Counts and percentages will be presented for participants in the FAS for:

- Participants with a positive nasopharyngeal swab for SARS-CoV-2 PCR on Day 1
- Participants seroconverting to SARS-CoV-2 between Days 1 and 57

Any participant who is positive for IgG Nucleocapsid assay for either matrix (SST or EDTA), will be considered SARS-CoV-2 positive.

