3.2 Secondary Endpoints

The secondary endpoints that will be evaluated to assess the Tasso+™ user experience and to perform a surveillance study for SARS-CoV-2 infection are:

Safety

- Percentage of eligible participants who experience solicited local AEs including pain, tenderness, redness, swelling, or bruising within 7 days of Tasso+™ administration
- Percentage of eligible participants who experience unsolicited AEs within 28 days of Tasso+™ administration

- Percentage of eligible participants who experience a related Grade 3 AE, a related Grade 4 AE, a related AE leading to discontinuation, or a related SAE within 28 days of Tasso+™ administration

Tolerability

- Percentage of eligible participants who complete last Tasso+™ administration (Day 57)

Usability

- Ease of use as assessed by the participant completing the Tasso questionnaire immediately following administration (on Days 1, 29, and 57) and on Day 85

SARS-CoV-2 infection surveillance

- Percentage of eligible participants with a positive nasopharyngeal swab for SARS-CoV-2 PCR on Day 1
- Percentage of eligible participants seroconverting to SARS-CoV-2 between Days 1 and 57

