Each Tasso+™ capillary blood collection will be followed by a 28-day follow-up period during which safety of the Tasso+™ device will be assessed using an eDiary (Symptom questionnaire). Solicited symptoms will be assessed for the first 7 days following each Tasso+™ administration, while unsolicited AEs will be captured for the full 28-day period after each administration.

Each self-collected Tasso+™ blood sample will be assessed for sample integrity by the Central Laboratory. Moreover, on Day 1, the self-collected capillary blood sample will be compared to a venous blood sample collected by an HCP, in order to assess device performance.

Each participant will receive nasopharyngeal swabbing on Day 1 for SARS-CoV-2 PCR testing to identify any baseline SARS-CoV-2 infections. The nasopharyngeal swab will be performed and resulted by the Site. Participants with positive results may remain on study but will be referred to their primary physician for COVID-19 management. During the study, if participants experience any COVID-19 symptoms or if they became COVID-19 positive, they are to be reported to the Investigator via provided Site's phone number. Management of COVID-19 positive participants is detailed in [Section 4.4](#). SARS-CoV-2 antibody testing (Days 1 and 57) will be conducted to serologically identify intervening COVID-19 cases, or if in the absence of intervening symptoms, SARS-CoV-2 infections.

The Study Schematic and Schedule of Assessments are available in [Figure 1](#) and [Table 1](#) respectively.

See [Section 7.4](#) for an overview of instruction for use (IFU) of Tasso+™ device. The detailed IFU will be provided in a separate document.

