5.2 Exclusion Criteria

A participant who meets any of the following exclusion criteria will not be eligible for participating in the study:

1. Medical history, or physical examination (including vital signs) findings, that suggest to the Investigator that the participant has undiagnosed or untreated medical condition(s) that could confound the AE evaluation and thereby undermine the study objectives.
2. Any known medical history of infection with HIV (CD4<200 and/or detectable viral load within the prior 3 months), hepatitis B (positive HBsAg), or hepatitis C (positive hepatitis C virus antibody).
3. Chronic illness for which a participant's immune system is suspected by the Investigator to be impaired or altered, such as cancer, autoimmune conditions, and diabetes.
4. Participation in another investigational study within 30 days of time of consent or plans to do so during the course of this study.
5. Large tattoos or skin eruptions overlying either of the deltoid muscles that could confound the monitoring for local reactogenicity following Tasso+™ administrations.
6. Use of systemic immunomodulatory therapy, including oral corticosteroids, within the past 6 months; or planned use of medications or nutritional supplements known to

or which potentially could affect organ function within 30 days prior to screening until end of study.

7. Acute illness within 14 days prior to device use unless it is determined by the Investigator that the illness is mild in severity and unlikely to progress.
8. Of limited legal capacity.
9. Any condition (including suspected alcohol- or drug-related addiction) that precludes adequate understanding, cooperation, and/or compliance with study procedures or any condition that could pose a risk to the participant's safety per Investigator judgment.

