6.3.1 Full Analysis Set (FAS)

The FAS is defined as all participants who administered Tasso+™ either in a site-supervised, proctor-supported, or unsupported setting. This analysis set will be the primary set used for analyses/summaries of the primary endpoint, as well as for secondary endpoints of seroconversion.

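### SAP 9.5.3.4 gives seroconversion only as a percentage of the whole FAS; a percentage among participants seronegative on Day 1 should be added

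*SAP*

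**What the plan says.** Protocol 3.2 lists as a secondary endpoint the "Percentage of eligible participants seroconverting to SARS-CoV-2 between Days 1 and 57". SAP 9.5.3.4 introduces its surveillance outputs with "Counts and percentages will be presented for participants in the FAS for" and then lists "Participants seroconverting to SARS-CoV-2 between Days 1 and 57". Protocol 9.4.2.4 says the same.

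The FAS, under protocol 9.2 and SAP 6.3.1, is everyone who administered the device in any setting. SAP 6.3.1 adds: "This analysis set will be the primary set used for analyses/summaries of the primary endpoint, as well as for secondary endpoints of seroconversion".

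For serostatus, SAP 9.5.3.4 gives one rule: "Any participant who is positive for IgG Nucleocapsid assay for either matrix (SST or EDTA), will be considered SARS-CoV-2 positive". Table 1 has a version of that rule for the capillary tubes (note l) and another for the venous tubes (note m). Venous blood is drawn on Day 1 only, so Day 57 status can come only from capillary tubes.

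Protocol 4.1 states the purpose: "SARS-CoV-2 antibody testing (Days 1 and 57) will be conducted to serologically identify intervening COVID-19 cases", or infections where there were no symptoms. The Day 1 PCR swab has a separate purpose, "to identify any baseline SARS-CoV-2 infections".

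**The concern.** A participant who already has nucleocapsid antibody on Day 1 cannot seroconvert by Day 57. Such participants may be enrolled. The infections named in exclusion criterion 2 (protocol 5.2, beginning "Any known medical history of infection with HIV") are HIV, hepatitis B and hepatitis C; past COVID-19 illness is recorded as history; and protocol 4.4 lets PCR-positive participants continue. The FAS does not remove them either.

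The planned percentage therefore combines two things: how many participants entered already seropositive, and how often the rest became infected. Only the second matches the purpose in protocol 4.1. Two studies with the same infection rate among susceptible participants could report different percentages solely because entry seropositivity differed.

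Three smaller gaps affect the same number. Seroconversion is not spelled out as negative on Day 1 to positive on Day 57. The Day 1 sample set is not named. The rule against imputing missing data (protocol 9.4.7, SAP 7.3) does not say whether someone without a valid result on either day stays in the denominator.

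**Working it through.** **Plan's own figure.** The documents state no expected seroconversion rate, precision or Day 1 seropositivity, so there is nothing to reproduce. The one figure used below is the planned enrolment of about 200 (133 + 67, SAP 6.2).

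**Is there a hidden restriction?** The word eligible in protocol 3.2 might look like one. The same word introduces the safety, tolerability and Day 1 PCR endpoints, so it means eligible for the study. The either-matrix rule sets positivity at one time point and supplies no denominator. No section limits the percentage to Day 1 negatives.

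**Formula.** Let N be the FAS size, s the share positive on Day 1, and r the seroconversion rate among those negative on Day 1. With complete results on both days:

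- converters = r × N × (1 − s)
- FAS percentage = converters / N = r × (1 − s)
- at-risk rate / FAS percentage = 1 / (1 − s), provided someone converts

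**Numbers.** N = 200 is the planned figure; s and the 5 converters are assumptions.

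| Assumed s | Negative on Day 1 | 1/(1 − s) | 5 converters, % of FAS | 5 converters, % at risk |
|---|---|---|---|---|
| 0% | 200 | 1.00 | 5/200 = 2.5% | 5/200 = 2.5% |
| 25% | 150 | 1.33 | 2.5% | 5/150 = 3.3% |
| 50% | 100 | 2.00 | 2.5% | 5/100 = 5.0% |
| 75% | 50 | 4.00 | 2.5% | 5/50 = 10.0% |

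Conversely, a fixed at-risk rate of 5% (assumed) appears as 5.00%, 3.75%, 2.50% or 1.25% of the FAS for the same values of s. If s = 0 or nobody converts, the two percentages agree.

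**Missing results.** Anyone in the FAS without a valid result on either day is also outside the evaluable at-risk group, so the formula needs both days complete. As an example with assumed values, take s = 50%, r = 5%, and 10% of Day 57 results missing for reasons unrelated to serostatus or infection. That leaves 100 × 0.9 = 90 evaluable negatives and an expected 4.5 converters. This is 4.5/200 = 2.25% if the missing participants stay in the denominator, and 4.5/90 = 5% of those evaluable. Missing Day 1 results widen the gap in the same way.

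**Day 1 sample set.** If note l and note m give different Day 1 answers for a participant who is positive on Day 57, that participant is a converter under one set and not under the other. Unlike the denominator, this choice can change the count.

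**The case against.** The strongest reply is that the SAP reports exactly the endpoint the protocol defines. The protocol asks for a percentage of eligible participants and promises no at-risk rate; identifying intervening cases is served by the count, which the denominator does not touch. This stands: the FAS percentage is not a miscalculation and should be kept. It does not make the FAS percentage interpretable as an infection rate, which is how many readers will take it.

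Seroconverting ordinarily means negative to positive, and note l is attached to the Tasso+ tubes on Day 1 as well as Day 57, so a capillary-to-capillary comparison is a natural reading. That also has force: these are mostly gaps in wording. But SAP 9.5.3.4 does not say so, and note m supplies a second Day 1 status.

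Three stronger readings are tempting but not supported.

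- A reader might infer that the at-risk rate could never be recovered from the report. That goes too far. SAP 4.0 promises individual results, SAP 9.0 summarises categorical variables by counts and percentages by default, and the contingency coefficient in SAP 9.5.2.2 requires a Day 1 cross-classification. What can be said is that no Day 1 serostatus table is explicitly specified.
- A reader might infer that this trial's figure will be too low by a factor of 2 or 4. The documents give no Day 1 seropositivity, so those factors are arithmetic on assumptions.
- A reader might infer from protocol Table 3 that capillary tubes would miss Day 1 positives here. Those data do not show it. Numbers tested differ between methods (35/49 venous against 31/48 Tasso on Day 4; 43/48 against 42/49 on Day 8), Day 1 is identical at 27/48, and the samples were whole blood run on another platform.

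**Conclusion.** The point holds as a limited one. As written, the plan gives a seroconversion percentage that falls below the at-risk rate whenever at least one FAS participant is positive on Day 1 and at least one converts. With complete serology on both days the ratio is 1/(1 − s): 1.00 to 4.00 over an assumed s of 0% to 75%. The actual size is unknown because s is not in the documents.

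The consequence is confined to interpreting one descriptive secondary endpoint. SAP 9.5.1 rules out hypothesis testing and the sample size has no formal basis (SAP 6.1), so no test or power statement is affected. The change is worth making because it is cheap and uses data already planned.

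**What to change.** In SAP 9.5.3.4:

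- Keep the FAS count and percentage. Beside them, add the percentage among FAS participants who are IgG-nucleocapsid negative on Day 1 and have a valid Day 57 result.
- Report the numbers positive on Day 1, with no valid Day 1 result, and with no valid Day 57 result. Show the last among Day 1 negatives, so that each participant falls in one group and the two denominators reconcile.
- State that seroconversion means negative on Day 1 to positive on Day 57.
- Name the Day 1 sample set (capillary under note l or venous under note m), choose it without reference to the seroconversion results, and show the other set as a sensitivity result.
- As optional context, give the number of converters who were PCR positive on Day 1, since protocol 4.1 treats those as baseline infections.

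The cost is a few sentences and some programming. No protocol amendment appears necessary: protocol 9.1 lets the SAP expand on the protocol, and SAP 9.5.3.2 already does so for tolerability. There are two downsides. The added percentage has a smaller denominator and is less precise: one participant is 0.5 points of 200 but 1.0 point of 100. The change also comes late: SAP 9.5.2.1 in version 2.0 already refers to Cohort B Day 1 records in the past tense, and protocol 9.1 says analysis personnel are unblinded. It should therefore be labelled as made after data collection.
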